8.6 DATA SAFETY MONITORING BOARD (DSMB)

A Data Safety Monitoring Board (DSMB) charter will be created that will specify all of the rights and duties of the DSMB. The DSMB Chair and the PPI will draft the DSMB charter with input from the biostatistician. This protocol is not meant to supersede that document and the terms of that document will take priority over any conflicting terms or statements listed within this study protocol.

The DSMB will meet (in person or virtually) periodically (at least annually) to review the progress of this study (e.g enrollment, site performance, data quality, meeting risk factor targets) as well as data on the safety of both treatment arms (e.g. complications of LDIVH infusion). Before the study begins, the DSMB will decide on the frequency and timing of interim safety analyses. The DSMB may recommend termination of the study if the LDIVH treatment arm is found to be unsafe. The DSMB may also recommend protocol revisions to address enrollment, safety, etc. There will be no interim analysis of efficacy by the DSMB. The DSMB may also recommend modifications to the protocol if reversible safety issues are identified. The primary principal investigator ([name]) may attend the DSMB meetings as a resource to the DSMB, but will not be allowed to vote and may be dismissed from the meeting(s) at anytime by the DSMB chair. The primary principal investigator will always be dismissed if there is any discussion of unblinded outcome measures. After each meeting, the DSMB Chair will prepare a letter to the study's primary principal investigator ([name]), Steering Committee, and site investigators, which will document the safety review that took place at the meeting. This letter will indicate whether or not there are any safety concerns. This letter will be provided to any of the IRBs at participating sites at their request. Safety of study participants is of the utmost importance.

9. CRITERIA FOR INTERVENTION DISCONTINUATION

9.1 TEMPORARY INTERRUPTION OF THE STUDY DRUG

It may become necessary to temporarily stop the study drug infusion during the course of this study.

- The attending physician investigator responsible for the patient will give permission to stop the study drug.
- For minor procedures not involving the CNS (e.g., tracheostomy, central line) the LDIVH infusion does not need to be stopped as long as the last set of coagulation labs were considered to be at a safe level to perform the procedure.
- For a minor procedure involving the CNS (e.g., ventricular drain, lumbar puncture, lumbar drain) the LDIVH infusion will be discontinued 3-6 hours before performing the procedure then resumed at least 3-6 hours after the procedure is completed if there were no bleeding complications associated with the procedure. For all ventricular drain placements or ventricular drain repositioning a new head CT will need to be obtained that shows no hemorrhagic complication prior to restarting the LDIVH. If there is a new asymptomatic intracranial hemorrhage related to ventricular drain insertion or positioning, then a follow-up head CT will need to be obtained 12 hours later. If the hemorrhage is stable on follow-up head CT then the LDIVH infusion can be resumed.
- Suspensions in administration of the LDIVH will be noted, and an adverse event/adverse drug reaction form will be completed if the drug is held due to hemorrhagic complication.
- LDIVH infusion can be resumed 12 hours after craniotomy assuming a head CT following craniotomy shows no concern.
- Resumption of LDIVH after any other procedures will wait a minimum of 3 hours.

All interruptions of the study drug infusion will be documented on the appropriate CRF. This will include the date of the interruption, the duration of the interruption, the reason for the interruption, and the rate of infusion at which the study drug was resumed.

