STUDY POPULATION	
Patients with a supratentorial aSAH secondary to a ruptured cerebral aneurysm that has been secured by endovascular coil embolization. Study subjects must score as a WFNS SAH grade ≤ 2 post-coiling with no significant aphasia at the time of enrollment and have a significant hemorrhage burden on the initial head computed tomographic (CT) scan that demonstrates a modified-Fisher grade 3, or grade 4 (with minimal intraparenchymal blood or IVH less than 25%.)

CLINICAL SITES	
Eight to ten designated clinical sites in the USA.

PLANNED ENROLLMENT	
88 patients (44 in each treatment allocation group; Approximately 5-6 patients per site per year average)

STUDY DURATION	
3 years [2 years enrollment; 3 months primary end-point follow-up visit; 3 months data analysis and reporting of results; 1-year follow-up visit secondary endpoint].

PRIMARY SAFETY ENDPOINT	
Rate of “Major Bleeding” or “Clinically Relevant Non-Major Bleeding” as defined by the International Society of Thrombosis and Haemostasis (ISTH) between the groups from enrollment until discharge from the acute inpatient setting.

SECONDARY SAFETY ENDPOINT	
Rate of Symptomatic Intracranial Hemorrhage between the two groups from enrollment until discharge from the acute inpatient setting. A symptomatic hemorrhage is defined as a 4-point or greater increase in the NIHSS or a decrease in the GCS by 2 or more points not explained by other causes.

ADDITIONAL PRESPECIFIED SAFETY OUTCOMES TO BE ANALYZED	
Rate of any new intracranial hemorrhage between the two groups from enrollment until discharge from the acute inpatient setting.
 
Rate of Serious Adverse Events (SAEs) between the two groups from enrollment until

the 90-day follow-up visit as reported by each site and adjudicated by an independent Clinical Events Adjudication Committee (CEC).

Rate of Type II Heparin Induced Thrombocytopenia (HIT) between the two groups from enrollment until the 90-day follow-up visit

Rate of DVT or PE between the two groups from enrollment until the 90-day follow-up visit

All cause and neurological mortality rates between the two groups from enrollment until the 90-day follow-up visit

PRIMARY CLINICAL EFFECT ENDPOINT

Mean Montreal Cognitive Assessment score (MoCA) at 90 (± 10) days post enrollment.

SECONDARY ENDPOINTS:

-PRIMARY BIOMARKER ENDPOINT

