6.14 Post-Infusion (Pre-Discharge) Head CT

A post-infusion head CT is required by this protocol. Most centers will perform a head CT during the later phases of the acute admission to evaluate for development of delayed hydrocephalus and / or to obtain a baseline scan prior to discharge. As a result, this scan will be considered part of the SOC and will not be funded by the study. We prefer the timing of this scan to be 12 hours (\pm 12 hrs) after completion of the study drug infusion (or an equivalent time period in the control group) to allow for comparisons to the post-procedure (pre-enrollment) head CT. If the patient's hospital discharge is planned for a time period < 24 hours after the cessation of the study drug infusion, the CT scan should be obtained prior to discharge.

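### Section 9.1 makes head CT after ventricular drain procedures a condition of restarting LDIVH, with no matching requirement for controls, yet any new intracranial hemorrhage, silent bleeds included, is compared between arms

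*Protocol*

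**What the plan says.** **Outcome.** The synopsis (section 1.1) lists among its additional prespecified safety outcomes: "Rate of any new intracranial hemorrhage between the two groups from enrollment until discharge from the acute inpatient setting". The secondary safety endpoint is separate: "Rate of Symptomatic Intracranial Hemorrhage between the two groups from enrollment until discharge from the acute inpatient setting". The first outcome is not limited to symptomatic events or to particular scans, so it takes in silent bleeds.

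**Scans in the LDIVH arm.** Section 9.1 deals with temporary interruption of the study drug. It states: "For all ventricular drain placements or ventricular drain repositioning a new head CT will need to be obtained". The same sentence makes the scan a condition of resuming the drug: "a new head CT will need to be obtained that shows no hemorrhagic complication prior to restarting the LDIVH". If the scan shows a new asymptomatic hemorrhage linked to the drain, "then a follow-up head CT will need to be obtained 12 hours later". It also states: "LDIVH infusion can be resumed 12 hours after craniotomy assuming a head CT following craniotomy shows no concern".

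**Scans in both arms.** Section 6.3 requires a CT after coiling and before enrollment. Section 6.14 states: "A post-infusion head CT is required by this protocol", with an equivalent time window for controls. The schedule in section 15.1 shows no other head CT after enrollment.

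**Control arm otherwise.** Section 6.8 gives controls no study infusion, and section 6.12 leaves their management largely to local standard of care.

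**The concern.** How often a silent hemorrhage is recorded depends on how often the head is scanned. Here one arm has a mandated search at the moment a silent bleed is most likely, just after a catheter has been passed or moved, because the drug cannot be restarted without it. The other arm is searched at that moment only if the site chooses to. With identical true bleeding risk, the recorded rate could then be higher on LDIVH.

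This matters because safety is the first primary objective and the trial is meant to inform whether a Phase III study is warranted. An excess of intracranial bleeding on heparin would weigh in that decision, and it could not be separated from an excess of scanning. The blinded core lab does not remove the problem: blinding equalizes how scans are read, not which scans exist.

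**Working it through.** The plan states no figure on this point, so there is none to reproduce. The check has two parts.

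**1. Head CT rules by arm**

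| Occasion | LDIVH | Control |
|---|---|---|
| After coiling, before enrollment (6.3) | required | required |
| After drain placement or repositioning (9.1) | required before restart | not stated; site practice |
| 12 hours after a silent drain-related bleed (9.1) | required before restart | not stated; site practice |
| After craniotomy (9.1) | condition of resuming | not stated; site practice |
| Post-infusion / pre-discharge (6.14) | required | required |

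The three middle rows are the asymmetry. After enrollment, only the last row is common to both arms.

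**2. Illustration of size, with no true drug effect**

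The one input from the protocol is 44 patients per arm. The rest are assumptions, because the documents give none of them:
- *e*, share with a drain procedure during the infusion period: 10% to 50%
- *h*, silent-bleed risk in such a patient, the same in both arms: 10% to 30%
- *d*, chance that a control's silent bleed is still seen on a usual-care or discharge CT: 0.25 to 0.75, with 1.0 as reference
- *b*, other new intracranial hemorrhage, the same in both arms: 3%

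Detection on LDIVH is taken as 1. Then:
- recorded rate on LDIVH = *b* + *e·h*
- recorded rate in controls = *b* + *e·h·d*
- artificial excess = *e·h·*(1 − *d*)

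| Case | LDIVH | Control | Excess | Patients of 44 | Ratio |
|---|---|---|---|---|---|
| Low: *e* 0.1, *h* 0.1, *d* 0.75 | 4.0% | 3.75% | 0.25 points | 0.11 | 1.07 |
| Middle: *e* 0.3, *h* 0.2, *d* 0.5 | 9.0% | 6.0% | 3.0 points | 1.32 | 1.50 |
| High: *e* 0.5, *h* 0.3, *d* 0.25 | 18.0% | 6.75% | 11.25 points | 4.95 | 2.67 |
| Any *e*, *h* with *d* = 1 | equal | equal | 0 | 0 | 1.00 |

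Middle case in full: 0.03 + 0.3 × 0.2 = 0.09; 0.03 + 0.3 × 0.2 × 0.5 = 0.06; difference 0.03; 44 × 0.03 = 1.32.

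The chance of a significant false excess on LDIVH was found by exact binomial enumeration with a two-sided 5% Fisher test. It is 0.2% in the low case, 2.5% in the middle case (0.8% with the same *e* and *h* at *d* = 1) and 25.5% in the high case. In most of the range the harm is a distorted estimate rather than a false significant result.

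**The case against.** **Control practice is unknown.** The protocol neither requires nor forbids a CT after a drain procedure in controls. If every site does one anyway, the bias is zero. This stands, so the bias is conditional. The protocol does nothing to secure equal scanning, however.

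**The exposure is limited.** Drains already in place at enrollment fall outside the restart rule, the common post-infusion CT can still show bleeds that have not cleared, and same-admission clipping is an exclusion, so the craniotomy condition adds little. All of this stands and reduces the size.

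**The outcome ranks low.** It is neither primary nor secondary and is not in the study-success definition, and the error is toward overstating harm. This also stands. Part of the remedy is detail that a statistical analysis plan could hold, but the unequal scanning comes from the protocol itself.

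**Stronger readings that the protocol does not support**
- *That the primary safety endpoint is inflated.* A reader might infer that holding LDIVH for a CT-only bleed counts as clinically relevant non-major bleeding. Section 8.5 does include a change of study drug for bleeding, but only where the bleeding is clinically overt. A silent CT finding does not plainly meet that, and the infusion is already off for the procedure.
- *That drain-tract hemorrhage is a leading source of the 10-20% background bleeding.* Section 8.5 names it in an unranked list of examples and gives no share.
- *That apparent risk doubles.* With no other hemorrhage and *d* = 0.5, 20% × 20% gives 4% versus 2%. That ratio is simply 1/0.5, the detection assumption restated, and amounts to 1.8 versus 0.9 patients of 44.

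**Conclusion.** The asymmetry is plain in the text: post-drain head CTs are mandated as a condition of restarting LDIVH, have no control counterpart, and feed an outcome compared between arms that counts silent bleeds. If sites scan controls less after drain procedures, the comparison leans against heparin. Under the model used, detection alone cannot push it the other way.

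The size cannot be determined from the documents. The illustrations run from zero with equal scanning to about 11 points at an extreme corner, with about one patient of 44 in a middle case. They rest on the assumed drain frequency, silent-bleed risk, control detection and 3% background rate. This is a weakness in one additional prespecified safety outcome. It does not show that the primary safety endpoint is biased, and it is worth correcting mainly because the correction is cheap.

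**What to change.** 1. For any new intracranial hemorrhage, define an arm comparison that uses the blinded core-lab read of the post-infusion CT against the pre-enrollment CT, both required in both arms, plus symptomatic hemorrhage at any time from enrollment to discharge. Report by arm how many patients lack the post-infusion scan.
2. Report all detected hemorrhages as well, so that no safety information is lost, and tabulate separately the asymptomatic ones found only on LDIVH restart CTs.
3. Report the number of head CTs per patient by arm, so that readers can judge how unequal the search was.
4. Do not remove restart-CT bleeds from the clinically relevant non-major count. That would drop events from one arm only of the primary safety endpoint. Apply the section 8.5 definition, including the clinically overt condition, identically in both arms.

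Cost: outcome wording, a core-lab hemorrhage item if its form does not already hold one, and one or two tables. No scan is added and no imaging or infusion rule changes. The downside is that small bleeds that clear before the post-infusion CT are described rather than compared. The restricted comparison reduces the ascertainment bias; it does not make the two arms' usual care identical.

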9.2 EARLY DISCONTINUATION OF THE STUDY DRUG

It may become necessary during a patient's enrollment that the study drug infusion be discontinued for patient safety reasons. Reasons for early discontinuation of the study drug infusion will be recorded in the appropriate CRF, as well as any AEs, SAEs, or UAEs that occurred.

9.3 WITHDRAWAL FROM THE STUDY

Subjects may withdraw from the study at any time for any reason with no penalty or loss of benefits they are otherwise entitled to. The patient will suffer no change in their non-study related medical care as a result of this decision. They will not be penalized in any way either directly or indirectly. If a patient chooses to withdraw from the study, the study team will be notified as soon as possible so that additional data collection will terminate.

10. DATA ANALYSIS AND CONSIDERATIONS

10.1 Sample Size Justification and Primary Clinical Effect Analysis

The sample sizes justification is based on the combination of the pilot data that we have previously observed ([name] Unpublished) and results based on Schweizer et al. (2012). Two main outcomes, MoCA and MMSE, were compared by Schweizer et al (2012) and their validity was compared. The two measures have slightly different cut-offs for defining impairments (MoCA score <26 and MMSE score <27). In this study we will use MoCA as a primary outcome measure. Based on published data, MoCA has mean (SD) of 25.4 (2.8) with n=32. In our pilot data with small sample sizes, we observed an overall mean of 24.6 (5.4) with n=47. The separate group means were 26.4 (2.3) with n=25 and 22.7 (7.0) with n=22 in the treatment and control arms, respectively. Because the two groups were heterogeneous, we assume SD=2.5 in treatment group and SD=7.0 in control group. As hypothesized and as documented in the preliminary data, MoCA is higher in the treatment arm than in the control arm, and so we will use one-sided test procedures. The study design is that of a two group, multicenter randomized clinical trial.

Table S1: Sample sizes based on having alpha=5% and SD1=7.0 and SD2=2.5 to detect 3 unit (effect size=0.5 SD) using one-sided two-sample t test with unequal variances.

Power	N1	Total N
80%	40	80
85%	46	92
90%	54	108

Given the number of centers participating, we plan to enroll 40 evaluable subjects in each arm. Assuming 8 centers, a sample size of 80 would be realized by recruiting 10 per center. Note that we need to balance the number of treatment and controls to be equal at each center, but not necessarily having equal number of subjects at each center. However, the numbers in the tables do not adjust for loss to follow up, drop outs, the ability to adjust for covariates, or for the loss of degrees of freedom for the centers in a test or model. The discussion below addresses further aspects of the sample size consideration.

Based on a desired total of 40 patients per arm, and an assumed dropout rate of 10%, the trial would require 44 patients in each arm for a total enrollment plan of 88 patients distributed over 8 sites, or on average 11 patients per site. There are multiple covariates that may confound the findings and this needs to be addressed in the design of the study. The primary factors are: center, risk associated with anterior communicating artery (ACoA) aneurysm location (1 versus others), age (≤ 70 versus > 70) and sex. The other factors are: fever (yes, no), transfusion (yes, no), vasospasm (yes, no). Due to limited resources only primary factors (ACoA, group and sex) will be considered to balance the allocation of treatment and control in 1:1 ratio. Thus, the randomization will be balanced within each of 6 strata. Advanced age will be controlled for by eliminating enrollment for patients over 70 years. Effect of the remaining factors will be addressed in the multi-variate model.

We will also compare the frequency of severe cognitive impairment (MoCA ≤ 20) in the two arms. Previous data demonstrated a rate of 0% (0/25) severe cognitive impairment in the heparin treatment group and approximately 32% (7/22) in the control group. In our currently planned study, we will assume a 5% rate of severe cognitive impairment in the heparin treatment group and a 32% rate of severe cognitive impairment in the control group. This will also allow a demonstration of power = 80% with alpha at 0.05 for our previously calculated sample sizes ($n_1=40$ and $n_2=40$) using a two-sample one-sided binomial test. This binomial calculation provides a second sample size estimate that supports our previous estimate of needing 40 patients per group. Therefore the final sample size estimation will be placed at a total of 88 patients to account for a 10% dropout rate leaving a final number of patients available for primary outcome analysis of 80 patients. Drop-out will be monitored during the enrollment process. If we approach 8 patients lost to follow-up then additional enrollments (beyond 88) will be considered if funding is available.

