1.2.2 Secondary Objectives

1. Measure the correlation between blood / CSF levels of inflammatory biomarkers (e.g. hsCRP, IL-6) and cognitive function (MoCA).
2. Demonstrate a reduction in blood / CSF levels of inflammatory biomarkers (e.g. hsCRP, IL-6) in the LDIVH treated subjects compared to controls.
3. Demonstrate a reduction in cerebral vasospasm in the LDIVH treated subjects compared to controls by measuring the proportion of patients in each group who:
 - i. Demonstrate moderately severe or severe angiographic vasospasm by CTA or DSA obtained within the prime vasospasm window
 - ii. Demonstrate moderately severe or severe vasospasm on transcranial Dopplers (TCDs)
 - iii. Demonstrate vasospasm related CT infarctions
4. Demonstrate a reduction in “Delayed Cerebral Ischemia” as defined by the Neurocritical Care Society:
 - i. Symptoms of neurological deterioration (e.g., hemiparesis, aphasia, altered consciousness) presumed to be related to ischemia
 - ii. Symptoms persist for more than one hour
 - iii. Symptoms cannot be explained by other physiological abnormalities
5. Demonstrate a reduction in the need for “rescue therapy” for delayed cerebral ischemia and / or symptomatic cerebral vasospasm
6. Demonstrate a difference between the LDIVH treated subjects and controls in the proportion of patients in each group who:
 - i. Have any fever (Temperature $\geq 38.3^{\circ}\text{C}$ / 101.0°F)
 - ii. Have multiple fevers (≥ 3 fever episodes)
7. Demonstrate a significant difference in “fever burden” between LDIVH treated subjects and control subjects
8. Demonstrate a difference between LDIVH treated subjects and controls in mean Daily Fever Burden during the LDIVH infusion.

9. Demonstrate better clinical outcomes in the LDIVH treated subjects compared to controls with one of the following measures:
 - i. mRS at 90 days and 1-year (Ordinal Regression Analysis)
 - ii. Barthel Index at 90 days
 - iii. Center for Epidemiologic Studies Depression Scale (CES-D) at 90 days and 1-year
 - iv. QOLIBRI-OS at 90 days and 1-year
 - v. Lawton IADLs at 90 days
 - vi. Trail Making Test Parts A&B at 90 days
 - vii. Return to Work Status at 90 days and 1-year
 - viii. MoCA at 1-year
10. Perform Pre-specified Subgroup Analysis of Outcome measures for LDVIH and Control groups using the following subgroup designations:
 - i. Sex (Male versus Female)
 - ii. Admission CT Hijdra Sum Score (<23 versus ≥ 23)

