 - iii. Aneurysm location (ACoA Aneurysm location vs. all others; any location; anterior circulation versus posterior circulation)
 - iv. Infection requiring Antibiotic Treatment versus no infection
 - v. Elevated hsCRP at enrollment vs. normal levels at enrollment
 - vi. WFNS 1 vs. 2
 - vii. Modified Fisher grade 3 and 4 while excluding accidental enrollments with Modified Fisher not equal to 3 or 4
 - viii. Chemical DVT prophylaxis: UFH 5000 units twice daily, or increased dose in obese patients according to SOC
 - ix. LDVIH arm: LDIVH infusion >10 days vs. ≤ 10 days
 - x. LDIVH arm: Initiation of LDIVH within 48 hours of hemorrhage ictus vs. > 48 hours
 - xi. LDIVH arm: Anti-Xa (Infusion Day 6) value < 0.20 IU/mL vs. ≥ 0.20 IU/mL
 - xii. Vasospasm related CT infarction vs. No vasospasm related CT infarction
 - xiii. Tobacco smoking versus no tobacco smoking

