2.2 Supporting Data in Humans

Recent retrospective human aSAH studies evaluating the Maryland low-dose IV heparin (LDIVH) protocol provide evidence that heparin may reduce the incidence of symptomatic vasospasm requiring rescue therapy, vasospasm related CT infarction, and cognitive dysfunction. In [name] et al. (J Neurosurg 119:1611-1619) an analysis of 86 Fisher grade 3 aSAH patients treated with craniotomy and clipping was performed. The patients were enrolled concurrently and 43 LDIVH patients were compared to 43 control patients. The incidence of clinical vasospasm in the control group was 47%, and 9% in the LDIVH group ($p=0.0002$). When evaluating for CT evidence of vasospasm related infarction, there was a 21% incidence of CT infarct in the control group, and 0% incidence of CT infarct in the LDIVH treated group ($p=0.003$).

There were no hemorrhagic complications. Unpublished study data ([name]) presented during a symposium at the 2015 AHA/ASA International Stroke Conference demonstrated a significantly better ($p=0.013$) mean MoCA score of 26.4 in the LDIVH treated group ($n=25$) compared to 22.7 in the control group ($n=22$). [MoCA score range 0-30, normal 26-30]. A 3-point difference in mean MoCA scores is considered clinically relevant. The influence of heparin on MoCA remained significant after controlling for potential confounding factors with multivariate regression analysis. Additional preliminary data demonstrate that the Maryland LDIVH protocol can also mute elevations of the inflammatory biomarker myeloperoxidase (MPO) at 48 hours ([name], unpublished data). MPO has been previously identified to be elevated in serum after aSAH and at even higher levels in those patients with cerebral vasospasm. The Maryland LDIVH protocol has been administered to over 200 patients without any serious adverse safety concerns.

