It is possible that UFH will modulate the inflammatory response to the point of reducing fever burden preferentially in the LDIVH arm. This may lead to improved clinical functional measures such as perseveration of cognitive function. It is also possible that a significant muting of the inflammatory response will limit the body's natural inflammatory mechanism to fend off infectious insults resulting in the possibility of unintended infectious complications which if not recognized early in their course (i.e., no heralding fever, elevated serum WBC count) could become more difficult to treat with antibiotics. However, this theoretical risk of increased infections as a result of improved fever control was not borne out in a study undertaken at Columbia University when comparing conventional fever control methods to aggressive fever control methods (Badjatia N et al. *Neurosurgery* 2010;66(4):696-700) and was not identified in more than 100 post-craniotomy patients treated with the LDIVH protocol.

This study will monitor fever episodes and overall daily fever burden. It will also track all infectious events and consider them adverse events (AEs) as well as track any anti-microbial therapies. The following recommendations are made to merge the goals of this study with the Neurocritical Care Society's Consensus recommendations:

- **The cause of fevers should be investigated and treated aggressively per the SOC at each clinical site based on guidelines set forth by the Society of Critical Care Medicine (SCCM) and the Neurocritical Care Society** which may include antimicrobials (for proven or suspected infections), other pharmacological agents and utilization of temperature modulation devices (TMDs).
- **The overall efficacy of most antipyretics is low and we prefer avoidance of acetaminophen and / or ibuprofen for fever control unless required per the SOC at the institution as these medications could confound our study results.** If these medications are deemed necessary per the SOC at the institution, then the dose, duration, and timing of the medications will be recorded in the EDC system and **statistical analysis will be done to determine if there is any confounding influence of these medications on the study results.**

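### Section 10.1 treats fever, transfusion and vasospasm as confounders in the MoCA model, though all three can arise after randomization and can be consequences of treatment; two treatment-effect subgroups share the fault.

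*Protocol*

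**What the plan says.** Protocol section 10.1 opens its covariate discussion with "There are multiple covariates that may confound the findings and this needs to be addressed in the design of the study". It names centre, ACoA location, age and sex as primary factors and continues: "The other factors are: fever (yes, no), transfusion (yes, no), vasospasm (yes, no"). ACoA location and sex are handled by stratified randomization, and age by the upper limit of 70 years. Then: "Effect of the remaining factors will be addressed in the multi-variate model". By subtraction, the remaining factors are centre, fever, transfusion and vasospasm. No baseline timing is attached to the last three.

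Other sections describe the same three events differently:

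- **Vasospasm.** Section 1.2.2, objective 3: "Demonstrate a reduction in cerebral vasospasm in the LDIVH treated subjects compared to controls".
- **Fever.** Objectives 6 to 8 in section 1.2.2 concern differences in fever between the arms. Section 6.12.6 adds: "It is possible that UFH will modulate the inflammatory response to the point of reducing fever burden preferentially in the LDIVH arm". It goes on to name preserved cognition as a possible result.
- **Transfusion.** Section 6.12.7 reports an association with worse cognition. It also makes any bleeding event treated with two or more units a major bleed, which is part of the primary safety endpoint (sections 1.1 and 8.5).

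The prespecified subgroups in section 1.2.2, item 10, include "Vasospasm related CT infarction vs. No vasospasm related CT infarction" and "Infection requiring Antibiotic Treatment versus no infection".

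Section 10.4 plans both a model-based contrast and a simple two-sample test for MoCA. The success definition in section 1.1 asks for a significant improvement in mean 90-day MoCA (or a significant biomarker reduction), with no significant difference in bleeding attributable to the treatment. It does not name the analysis that decides.

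**The concern.** Under randomization, an event that occurs after assignment cannot confound the assignment. It can only be a consequence of treatment, of prognosis, or of both. If heparin protects cognition partly by preventing vasospasm or fever, holding those events fixed removes that part of the benefit. If unmeasured severity drives both the event and the MoCA score, conditioning on the event also unbalances severity between the arms, even when the event itself does no cognitive harm.

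Subgroups defined by infarction or infection raise the same difficulty. The patients who infarct on heparin need not be comparable with those who infarct on control, so the within-subgroup difference is no longer a randomized comparison.

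What is at stake is the reading of the MoCA result. With no analysis named as decisive, a model adjusted for these events could be used to judge success, or could contradict the valid test with no rule for choosing between them.

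**Working it through.** **1. Reproduce the plan's own figure.** Inputs from section 10.1 and Table S1: difference 3 points, SDs 7.0 and 2.5, one-sided alpha 5%, 40 evaluable per arm, unequal-variance t test.

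- SE = √((7.0² + 2.5²)/40) = √(55.25/40) = 1.175
- Noncentrality = 3/1.175 = 2.55, with Satterthwaite df of about 49
- Power = 80.8%
- Smallest n per arm for 80%, 85% and 90% power: 40, 46 and 54, which is Table S1 exactly

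The trial is therefore sized for the unadjusted total effect.

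**2. What adjustment for vasospasm would do (illustration).** Section 2.2 gives "The incidence of clinical vasospasm in the control group was 47%, and 9% in the LDIVH group", a gap of 0.47 − 0.09 = 0.38. Let b be the MoCA loss caused by vasospasm. The protocol gives no value for b, so 2, 4 and 6 points are assumed.

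Adjusted coefficient = 3 − 0.38 × b.

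Power is computed in two ways: with the SE above, and with the SE inflated for the correlation between arm and vasospasm. For the second, the pooled vasospasm rate is (0.47 + 0.09)/2 = 0.28. Then R² = (0.38² × 0.25)/(0.28 × 0.72) = 0.0361/0.2016 = 0.179, and the variance inflation is 1/(1 − 0.179) = 1.22. Neither version credits the model with a smaller residual variance.

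| Assumed b | Removed (0.38 × b) | Coefficient left | Power, same SE | Power, with collinearity |
|---|---|---|---|---|
| 2 | 0.76 | 2.24 | 59% | 52% |
| 4 | 1.52 | 1.48 | 34% | 30% |
| 6 | 2.28 | 0.72 | 15% | 14% |

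The share of the 3-point effect removed runs from 0.76/3 = 25% to 2.28/3 = 76%.

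**3. Bias without any effect of vasospasm on MoCA.** In a large simulated sample, b was set to 0 and vasospasm held at 47% versus 9%. An unmeasured severity factor raised the log-odds of vasospasm by 1.0 per SD and lowered MoCA by 2 or 3 points per SD (all assumed). The unadjusted difference stayed at 3.0. The vasospasm-adjusted coefficient fell to 2.33 and 2.02 respectively.

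**4. Subgroups.** Vasospasm-related infarction is scored on post-infusion imaging and is itself an outcome (sections 1.1 and 1.2.2). Infections are tracked as adverse events, and section 6.12.6 raises the possibility that treatment affects infectious complications. Neither subgroup is restricted to what was known before randomization.

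**The case against.** The strongest reply is that the main comparison is not touched. Table S1 is built on a two-sample test, section 10.4 plans that test, and it keeps 80.8% power under the plan's assumptions. Section 10.4 also gives the multivariable models the purpose of examining prognostic factors, which is a legitimate use for in-hospital events. Vasospasm, fever and infarction are already compared between arms as outcomes. All of this stands, and it limits the point to the adjusted model and two subgroups. It does not remove the point: section 10.1, whose title covers the primary clinical effect analysis, gives confounding as the reason for including these factors, and nothing prevents the adjusted coefficient from being taken as the result.

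A reader might infer that the trial's power falls to 59%, 34% or 15%. The documents do not support that. Those figures apply to a hypothetical adjusted coefficient. They rest on an assumed MoCA loss and on vasospasm rates from clipped patients, whereas this trial enrols coiled patients, and the covariate itself is not defined beyond yes or no.

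A reader might also extend the criticism to the subgroups by infusion length (over 10 days or not) and by day-6 anti-Xa. Both are marked as LDIVH-arm only, so they are within-arm descriptions and not treatment-versus-control contrasts. They cannot bias the randomized comparison.

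Some fevers, transfusions or mild infections could precede randomization. The protocol does not restrict these variables to such cases, so this does not rescue them as baseline covariates.

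**Conclusion.** The protocol is wrong to class fever, transfusion and vasospasm as confounders and to place them, undated, in the MoCA model. This follows from its own objectives and its account of how heparin may work, and it does not depend on any assumed number. A coefficient adjusted for these events does not estimate the total effect the trial was sized for.

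The size of the distortion cannot be fixed from the documents. At the quoted vasospasm rates it is 0.38 points for each point of MoCA lost to vasospasm. That is about 0.8 to 2.3 of the 3 points over the assumed range of 2 to 6, with further bias possible from unmeasured severity.

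It would overstate the case to say that the plan as a whole loses or distorts its treatment effect, because the simple two-sample test remains valid. The practical exposure is that no analysis is named as decisive for study success. The infarction and infection subgroups have the same fault at lower stakes, since they do not enter the success definition.

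**What to change.** - In section 10.1, limit adjustment in the MoCA treatment-effect model to pre-randomization factors: sex, ACoA location, centre and, if wanted, age, WFNS grade and Hijdra score.
- In sections 1.1 and 10.4, state that the total-effect comparison of 90-day MoCA decides the MoCA part of study success, and name the test.
- Keep fever, vasospasm and infarction as outcomes. Use them and transfusion as explanatory variables only in a separately labelled exploratory prognostic or mediation analysis.
- In section 1.2.2, item 10, remove vasospasm-related infarction and infection requiring antibiotics from the treatment-effect subgroups, or label them non-causal description.

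The cost is wording in the protocol and in any statistical analysis plan. No new data, visits or patients are needed. The change should be made before the unblinded final analysis, because a choice between conflicting MoCA results made afterwards would not be credible.
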